6.1.1.2. Time of Follow-Up for MFS

A Kaplan-Meier summary table for MFS follow-up duration will also be generated to assess the follow-up time in the treatment arms by reversing the MFS censoring and event indicators.

6.1.1.3. Sensitivity/Robustness Analyses

The following sensitivity analyses will be performed for MFS.

Sensitivity 1: Including Events Regardless of Initiation of Antineoplastic Therapies

Censoring rules will follow those in the primary MFS analysis except that events occurring for the first time after the initiation of antineoplastic therapy will not be censored and be considered as events. A 2-sided stratified log-rank test (same as the primary analysis) will be used to compare the treatment groups.

Sensitivity 2: MFS on eITT Population

MFS for the eITT population will also be analyzed as a sensitivity analysis. The definition of MFS and censoring rules will be consistent with primary analysis. A 2-sided stratified log-rank test will be used to compare the treatment groups. All methods from the primary efficacy analysis will be repeated.

Sensitivity 3: MFS Based on Investigator Assessment

MFS as assessed by the investigator will also be analyzed as a sensitivity analysis. The definition of MFS and censoring rule will be consistent with primary analysis. A 2-sided stratified log-rank test will be used to analyze the MFS values. Furthermore, the concordance and discordance rates between the independent central radiology review and investigator assessment will be summarized using the metastasis status by the treatment groups.

Table 8 outlines the possible outcomes by investigator and BICR (Amit et al. 2011).

Table 8. Possible Outcomes for Investigator vs BICR

		BIC	CR
Investigator		PD	No PD
	PD	a = a1 + a2 + a3	b
	No PD	с	d

a1 = number of agreements on timing and occurrence of PD; a2 = number of times agreement on PD event but investigator declares PD event later than BICR; a3 = number of times agreement on PD event but investigator declares PD event earlier than BICR; PD = progressive disease.

N = a+b+c+d representing the number of patients in the FA population.

The timing agreement of progression has to be defined as a window of \pm 7 days.

The following measure of discordance/concordance will be calculated for each treatment arm:

- Total Event Discrepancy Rate: (b+c) / N
- Early Discrepancy Rate (EDR): (a3+b) / (a+b)
- Late Discrepancy Rate (LDR): (a2+c) / (a2+a3+b+c)
- Overall Discrepancy Rate: (a2+a3+b+c) / N
- Overall Concordance Rate: (a+d)/N

The EDR represents the positive predictive value of investigator assessment and quantifies the frequency with which the investigator declares progression earlier than BICR within each arm as a proportion of the total number of investigator assessed PDs.

The LDR quantifies the frequency with which the investigator declares progression later than BICR as a proportion of the total number of discrepancies within the arm.

Discordance metrics are calculated for each treatment arm. For each metric, the difference in discordance between the experimental and control arms is used to evaluate potential bias. If the discordance is similar across the treatment arms then this suggests the absence of evaluation bias favoring a particular arm. A negative differential discordance for EDR and/or a positive differential discordance for LDR may be indicative of investigator evaluation bias in favor of the experimental arm (Amit et al, 2011).

Sensitivity 4: Impact of Clinical Progression

In this sensitivity analysis, patients who discontinue study drug primarily due to clinical deterioration prior to protocol-defined evidence of radiographic progression will be considered as having clinical progression. For this analysis, MFS is defined as the duration of time between randomization and the earliest objective evidence of metastatic disease, date of study drug discontinuation for clinical progression, or death, or evidence of clinical progression, whichever occurs first. The censoring rules used for the primary analysis will be utilized. The hazard ratio and its 95% confidence interval will be reported.

Sensitivity 5: Impact of Censoring Due to Discontinuation Prior to Radiographic Progression for Patients Notified of PSA Progression or Progression by Positron Emission Tomography (PET) Imaging of Prostate-specific Membrane Antigen (PSMA)

For the censoring of MFS for the patients who reached PSA progression and discontinued study treatment prior to the development of radiographically detectable metastatic disease, and the potential for this to be informative censoring, a reference-based imputation method based on Bayes Gibbs sampling as outlined by Lu, Li, and Koch (Lu et al. 2015) will be implemented to assess the impact of the above censoring. If applicable, the inverse probability of censoring weighting (IPCW) method by Robins and Finkelstein may be used to adjust for the above censoring. For the censoring of MFS for the patients who discontinued

study treatment due to progression by PSMA-PET scan prior to the development of radiographically detectable metastatic disease, if applicable, the similar methods described above may be used to adjust for the censoring.

In order to assess the impact of patients initiating novel androgen inhibitors (such as enzalutamide, apalutamide, darolutamide and abiraterone) prior to the development of radiographically detectable metastatic disease, if applicable, the following sensitivity analyses may be performed: the Rank-Preserving Structural Failure Time Model (RPSFTM) (Robins & Tsiatis 1991), IPCW method (Robins & Finkelstein, 2000) and the two-stage method (Latimer & Abrams 2014).

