4.3. Evaluable Intent-to-Treat (eITT) Set

The evaluable ITT (eITT) set is defined as all ITT patients who have confirmed nonmetastatic disease at baseline by independent central radiology review. The eITT population will be used for certain efficacy analyses.

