5.2.4. Adequate Tumor Assessment

For soft tissues assessments by BICR, no assessments of CR, PR, or stable disease will be made given that the patient population is non-metastatic at study entry. The assessment options will be no disease (ND), no progression (NN), progressive disease (PD), or not evaluable (NE).

For bone assessment by BICR the assessment options will be No Bone Metastases (NBM), Bone metastases - unconfirmed (BPDu), Bone metastases (BPD), or NE.

For analyses based on BICR, a tumor assessment is defined as adequate when both bone and soft tissue assessments are evaluable (there is no NE in either bone or soft tissue) and the difference between bone and soft assessments dates is less than 25 weeks (of note, radiographic assessments are at 24 week \pm 5 days intervals in study schedule of activities). If either bone or soft tissue assessment is NE, the assessment would be considered as "inadequate".

For analyses based on investigator assessments, a tumor assessment is defined as adequate if both a bone scan and a soft tissue assessment are performed and the difference between bone and soft assessments dates is less than 25 weeks.

However, an assessment indicating PD from either a bone scan or a soft tissue assessment will be considered as adequate for declaring PD for analyses based on BICR and investigator assessment.

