The treatment effect will be estimated using a Cox's Proportional Hazard model stratified by the randomization strata to calculate the hazard ratio. Each stratum will define a separate baseline hazard function, ie, for the i-th stratum the hazard function is expressed as: $h(i;t) = h(i,0;t) \exp(x\beta)$, where h(i,0;t) defines the baseline hazard function for the i-th stratum and x defines the treatment arm (0 = control arm, 1 = experimental arm) and β is the unknown regression parameter.

Ties will be handled by using the Exact option in SAS.

In addition, the 95% CIs for the hazard ratio will be reported at the final analyses for MFS.

Kaplan-Meier estimates (product-limit estimates) will be presented by treatment arm together with a summary of associated statistics including the median MFS time with 2-sided 95% CIs. The CIs for the median will be calculated according to Brookmeyer and Crowley (1982) and the CIs for the survival function estimates at the time points defined above will be derived using the log-log transformation according to Kalbfleisch and Prentice (2011) with back transformation to a CI on the untransformed scale. The estimate of the standard error will be computed using Greenwood's formula.

Frequency (number and percentage) of patients with each event type (PD or death) and censoring reasons will be presented by treatment arm.

For patients not known to have had radiographic progression and who have not died at the time of the analysis data cutoff, MFS time will be censored at the date of the last adequate assessment (see Section 5.2.4) on or before the analysis data cutoff date. For patients who were randomized but later confirmed to have metastatic disease at enrollment or who had no adequate postbaseline tumor assessment, information will be censored on the date of randomization. Patients who initiate antineoplastic therapy such as cytotoxic chemotherapy, abiraterone acetate, hormonal agents, prostate cancer vaccines, nonradioactive bone-targeting agents and systemic radiopharmaceuticals for prostate cancer, or any antineoplastic therapy

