without evidence of metastasis will be censored at the last adequate assessment prior to initiation of such therapy. (Note: if progression occurs on the same date as the start of such therapy the progression will count as an event.) Additionally patients with documented progression or death after 2 or more missing tumor assessment will be censored at the last adequate assessment prior to the missing assessments. In this study, tumor assessments are assessed every 24 weeks. Therefore, time without adequate assessment is defined as 49 weeks (allowing for a +/-1 week window for assessments). The censoring rules for the primary and sensitivity analyses of MFS are summarized in Table 7.

Analysis	Censoring Rules	Date of Censoring
Primary analysis of MFS	Patients with no baseline or no post baseline assessments who have not died within 49 weeks after randomization	Date of randomization
	Patients who were randomized but confirmed metastatic at baseline	Date of randomization
	Patients who had no confirmed metastasis and did not die prior to data cutoff date	Date of the last adequate radiographic tumor assessment prior to data cutoff date
	Patients who initiate antineoplastic therapy such as cytotoxic chemotherapy, abiraterone acetate, hormonal agents, prostate cancer vaccines, nonradioactive bone-targeting agents and systemic radiopharmaceuticals for prostate cancer, or any antineoplastic therapy without evidence of metastasis	Date of the last adequate radiographic tumor assessment prior to first use of any such therapy
	Patients with radiation therapy performed for prostate cancer-related lesions without evidence of metastasis	Date of the last adequate radiographic tumor assessment prior to the earliest use of radiation therapy
	Patients with evidence of metastasis or death after 2 or more consecutive missed tumor assessment visits	Date of the last adequate radiographic tumor assessment prior to the first missed visit date

Table 7. The Censoring Rules for the Primary and Sensitivity Analyses of MFS

MFS = Metastatic Free Survival; of note, the censoring rules are applied to MFS events by either radiographic progression, or death due to any cause without evidence of radiographic progression; of note, antineoplastic therapies according to the above search criteria undergo medical review to confirm.

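### Protocol 10.4 censors patients found metastatic at enrolment at randomization in time-to-event analyses without exempting OS, which contradicts SAP 6.2.4; the sentence should be limited to the imaging endpoints before the final OS cut-off

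*SAP*

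**What the plan says.** **OS.** Protocol 10.4 has a general sentence, placed ahead of all the efficacy subsections, that censors patients later found to have been metastatic at enrolment at randomization in time-to-event analyses. It names no endpoint and exempts none. SAP 3.2.1.4 defines OS as time to death from any cause, and SAP 6.2.4 censors only patients without an event date, at last contact. SAP 5.1.2 says the final OS analysis takes an ITT approach. Protocol 18.9 says the same and that the analysis follows the SAP, but it also says OS is analysed as planned in Protocol 10.4.2, which sits under the 10.4 sentence.

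**MFS.** Here protocol and SAP agree. SAP 6.1.1.1 applies the rule in its text ("For patients who were randomized but later confirmed to have metastatic disease at enrollment") and in Table 7 ("Patients who were randomized but confirmed metastatic at baseline"); the censoring date is randomization. The evaluable ITT (eITT) set in SAP 4.3 is "all ITT patients who have confirmed nonmetastatic disease at baseline by independent central radiology review". Sensitivity 2 in SAP 6.1.1.3 reads: "MFS for the eITT population will also be analyzed as a sensitivity analysis. The definition of MFS and censoring rules will be consistent" with the primary analysis.

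**The concern.** The primary MFS analysis is complete, and SAP 5.1.2 says only OS will be formally tested at the final OS analysis. For that test the two documents give different rules for the same patients. Under the SAP, a patient found to have been metastatic at enrolment who later dies is an event. Under the literal protocol sentence he has zero follow-up and his death disappears. The sentence also leaves it unclear whether such a death counts toward the 271 deaths that trigger the analysis.

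On MFS the question is narrower. A patient censored at time zero is in no risk set, so leaving him out changes nothing. Sensitivity 2 therefore cannot show what setting these patients aside does to the hazard ratio.

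**Working it through.** **1. The plan's own OS power.** Inputs from SAP 5.1.1 and Table 3: 191 deaths in the two blinded arms, hazard ratio 0.67, final critical value 1.96001, 1:1 comparison. Formula: power = Φ(½·√d·|ln HR| − z).
- d = 191, α = 0.05: ½ × 13.820 × 0.4005 = 2.767; Φ(2.767 − 1.960) = 79.0%. The plan states 79.0%.
- α = 0.03 (z = 2.170): 72.5%, against 72.3% stated. α = 0.02 (z = 2.326): 67.0%, as stated.

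The plan's figures reproduce.

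**2. The literal Protocol 10.4 reading.** The documents do not say how many patients were found metastatic at enrolment or how many of them died. Assume 3 to 10 of the 191 deaths are lost and not replaced:

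| Deaths counted | ½·√d·\|ln 0.67\| | Power |
|---|---|---|
| 191 | 2.767 | 79.0% |
| 188 | 2.746 | 78.4% |
| 181 | 2.694 | 76.9% |

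If the 271-death trigger also left these deaths out, the cut-off would come later instead and little or no power would be lost. That is why the trigger needs the same clarification.

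**3. Where the rule appears in the SAP.** Within SAP 6.1 to 6.3 it is written for MFS (6.1.1.1 and Table 7) and time to distant metastasis (6.3.1). It is absent from time to PSA progression (6.2.2), new antineoplastic therapy (6.2.3), OS (6.2.4), castration resistance (6.3.6), symptomatic progression (6.3.7) and first symptomatic skeletal event (6.3.8). This fits a rule meant for the two imaging endpoints. The protocol sentence is broader than anything the SAP carries out.

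**4. MFS: which listed analyses lift the rule?**
- Sensitivity 1 relaxes only the antineoplastic-therapy censoring.
- Sensitivity 2 excludes these patients by definition. In simulated trials (712 men, 8 strata, 4 to 36 such men) the stratified log-rank statistic was the same whether they were censored at time zero or dropped; the maximum difference was 0.
- Sensitivity 3 uses investigator reads with the primary censoring. Table 7 does not say whose read confirms baseline metastasis, so a man metastatic only on central read might contribute here; the wording leans against it.
- Sensitivity 4 keeps the primary censoring.
- Sensitivity 5 and its optional extensions address stopping after PSA or PSMA-PET progression and use of novel androgen inhibitors.
- The COVID-19 options in SAP 6.9 address COVID-19 deaths and missed scans.

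None clearly lifts the rule.

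**5. A rough scale for MFS, on assumptions only.** Suppose 1% to 3% of the 712 men in the blinded arms (two thirds of 1068), so 7 to 21 men, were counted as early events, split evenly and with no treatment effect among them. The log hazard ratio shrinks by about 142/(142 + k):
- k = 7: exp(ln 0.58 × 142/149) = 0.60
- k = 21: exp(ln 0.58 × 142/163) = 0.62

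An uneven split between arms, which chance alone can produce, would move the ratio either way.

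**The case against.** The strongest reply is that the OS conflict is already settled. SAP Section 2 says the SAP may modify the protocol's plans, Protocol 10.4 itself leaves the analytical approach to the SAP, and Protocol 18.9 sends the final OS analysis to the SAP on an ITT basis. Most of this stands, and it is why the expected effect is nil. What remains is that Protocol 18.9 also points to Section 10.4.2, and a rule that would delete deaths from an alpha-controlled test should not stay in the protocol.

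On MFS the reply is stronger. The rule is deliberate, is stated consistently in both documents, and concerns men who did not meet Exclusion 1. MFS has little meaning for a man already metastatic at time zero. Central review before enrolment (Protocol 4.2 and Table 1) should keep the number small. The readout is complete, so any addition is post hoc.

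A reader might infer that Sensitivity 2 is redundant. It is not: eITT requires confirmed nonmetastatic disease, so it also drops men whose baseline read was unconfirmed or not evaluable, and some of those can contribute to the primary analysis. A reader might also infer that the primary MFS result is biased. Nothing in the documents shows that; baseline status precedes treatment, and no imbalance between arms is reported.

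**Conclusion.** The contradiction on OS is real as written and minor in consequence. If SAP 6.2.4 is followed, as is very likely, OS is unaffected. Under the literal protocol sentence the loss is about 0.6 to 2.1 percentage points of power. That rests on an assumed 3 to 10 lost deaths, no replacement, and the scenario with the full 0.05 available, which SAP 5.1.2 says applies. The documents do not support a claim that the final OS test will drop these deaths; they show only that one sentence permits that reading.

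The MFS point is secondary and optional. Patients confirmed metastatic at baseline contribute nothing to the primary analysis or to Sensitivity 2, and no other listed analysis clearly restores them. The number of such patients is not in the documents, so the hazard ratios of 0.60 and 0.62 above show scale only.

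**What to change.** **Required, before the final OS cut-off.** Limit the Protocol 10.4 sentence to MFS and time to distant metastasis. State there and in SAP 6.2.4 that every death in every randomized patient counts in the OS test and toward the 271-death trigger. The cost is one sentence in each document; no analysis changes if the SAP rule is already in use.

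**Optional, for MFS.** Keep Sensitivity 2 as it is. Report the number of these patients and their deaths by arm. The count should largely come from tables already planned: "Frequency (number and percentage) of patients with each event type (PD or death) and censoring reasons will be presented by treatment arm", and SAP 6.7.2 summarizes reasons for exclusion from populations. Their deaths are not separately tabulated, since SAP 6.8.2 gives deaths by arm only. A simple MFS run without the time-zero rule could be added, labelled post hoc. Its limits should be stated. Protocol 9.1.2 plans imaging only until metastatic disease is observed, so two other Table 7 rows ("Patients with no baseline or no post baseline assessments who have not died within 49 weeks after randomization" and "Patients with evidence of metastasis or death after 2 or more consecutive missed tumor assessment visits") could still return some of these men to randomization or discard later deaths.

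An event defined as a new lesion beyond those at baseline should not be required. SAP 5.2.4 says "no assessments of CR, PR, or stable disease will be made given that the patient population is non-metastatic at study entry", and the outcome categories it lists may not allow that comparison. Counting these men as day-1 events is not needed either, because it would mainly measure chance imbalance between arms. The optional work is one row of deaths and one re-run on existing data.

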6.2. Key Secondary Endpoint(s)

6.2.1. MFS Between Enzalutamide Monotherapy Versus Placebo Plus Leuprolide

MFS between enzalutamide monotherapy versus placebo plus leuprolide will be defined as above for primary analysis of the combination comparison. Analysis of this endpoint will be performed using the 2-sided stratified log-rank test to compare the 2 treatment groups with the same strata described in Section 6.1.1. A Cox proportional hazards model will be used to evaluate the MFS analysis to calculate the HR and its 95% CI.

The same sensitivity analyses as those specified for the primary comparison between enzalutamide in combination with leuprolide versus placebo in combination with leuprolide in Section 6.1.1 will be implemented.

6.2.2. Time to PSA Progression

Only results from PSA samples taken before the initiation of any new prostate cancer therapy and after the start of study drug will be considered.

PSA progression is defined in Section 3.2.1 as the date that a \geq 25% increase and an absolute increase of \geq 2 µg/L (2 ng/mL) above the nadir (or baseline for patients with no PSA decline by week 25) that is confirmed by a second consecutive value at least 3 weeks later. The date of PSA progression is the first date the PSA progression is observed. For patients who have suspended treatment at week 37 and later reinitiated treatment, baseline will be defined as the last PSA assessment prior to or on the date of reinitiation. The date of PSA progression is the first date the PSA progression is observed.

PSA progression is only defined during active study treatment; therefore, patients meeting PSA progression during the suspension period will be censored unless the PSA progression criteria are subsequently met following treatment reinitiation. Time to PSA progression will be censored on the date of the last PSA sample taken. Patients with PSA progression after 2 or more consecutive missed PSA assessments (ie, time interval >6 months or 182 days between 2 consecutive PSA samples) will be censored on the date of last PSA assessment prior to the missed assessments. In patients with no baseline PSA and patients with no postbaseline PSA results, time to PSA progression will be censored on the date of randomization.

Time to PSA progression will be compared between treatment groups using a 2-sided stratified log-rank test.

6.2.3. Time to First Use of New Antineoplastic Therapy

New antineoplastic therapy includes medications used specifically for prostate cancer treatment including hormonal treatments, immunotherapy, chemotherapy and investigative agents.

Time to first use of new antineoplastic therapy will be compared between treatment groups using a 2-sided stratified log rank test. In patients with no new antineoplastic therapy initiated for prostate cancer after randomization, time to start of new antineoplastic therapy will be censored on the last visit date or the date of randomization, whichever occurs last.

At the time of final analysis of OS, this endpoint will be summarized descriptively and provided as exploratory analysis.

